Appendix 3E: Registration, reporting, and publication policy**Trial disclosure**

LEO is committed to be transparent with respect to its clinical trials.

Basic information of this clinical trial will be registered in the global data registry, www.ClinicalTrials.gov before the first subject enters into the trial. The trial may also become registered in other online data registries, according to applicable law and regulations.

Results of this clinical trial will be posted on the corporate website of LEO in accordance with LEO's Position on Public Access to Clinical Trial Information no later than 12 months after trial completion. Trial results may also become reported in www.ClinicalTrials.gov, www.clinicaltrialsregister.eu and national data registries in accordance with applicable law and regulations after clinical trial completion or premature termination. LEO may also

provide researchers access to anonymised patient level data for further research. Publication and access will be in accordance with LEO's Position on Public Access to Clinical Trials which can be found on LEO's website.

Publications

The investigator shall be entitled to make publications of the results generated by investigator in accordance with the process described here.

A multi-centre publication will be submitted for publication within 18 months after the clinical trial has been completed or terminated at all trial sites and all data have been received, defined as database lock of the clinical trial. After such multi-centre publication is made public, or if no multi-centre publication has been submitted with the above-described deadline, the investigator shall have the right to publish the results from the clinical trial generated by the investigator, subject to the following notice requirements:

Prior to submission for publication or presenting a manuscript relating to the clinical trial, the investigator shall provide to LEO a copy of all such manuscripts and/or presentations. LEO shall have rights to review and comment. The investigator shall consider LEO's comments but is not required to modify the manuscript and/or presentation based on such comments, provided, however, that the investigator upon the request of LEO remove any confidential information (other than results generated by the investigator) prior to submitting or presenting the manuscripts. The investigator shall, upon the request of LEO withhold the publication or presentation to allow LEO to protect its inventions and other intellectual property rights described in any such manuscripts.

In case no multi-centre publication has been made public at the time of investigator's notification of an independent publication to LEO, LEO and the writing group may also delay the publication or presentation if the manuscript is deemed to harm the ongoing multi-centre publication.

In case of publications made by the investigator after the first multi-centre publication has been published, the above-mentioned requirements must still be followed.

Any publication must comply with Good Publication Practice (GPP3) standards.

LEO complies with GPP3 standards and the recommendations from the International Committee of Medical Journal Editors. LEO complies with the positions of the International Federation of Pharmaceutical Manufacturers & Associations (IFPMA), European Federation of Pharmaceutical Industries and Associations (EFPIA), Japan Pharmaceutical Manufacturers

Association (JPMA), Pharmaceutical Research and Manufacturers of America (PhRMA), and the joint position statement by the American Medical Writers Association (AMWA), the European Medical Writers Association (EMWA), and the International Society for Medical Publication Professionals (ISMPP) on disclosure of information about clinical trials, trial results and authorship. LEO also follows the CONSORT reporting guidelines (22).

Appendix 3F: Insurance

LEO has taken out relevant insurances covering the subjects in the present clinical trial in accordance with applicable laws and regulations.

Appendix 3G: Financial disclosure

Investigators will provide LEO with sufficient, accurate financial information as requested to allow LEO to submit complete and accurate financial certification or disclosure statements to the appropriate regulatory authorities. Investigators are responsible for providing information on financial interests during the course of the clinical trial and for 1 year after completion of the clinical trial, or for a longer period of time if required by local legislation.

Appendix 3H: Trial and site closure

Premature termination of trial or trial site

LEO, the investigator, the IRB/IECs or competent authorities may decide to stop the clinical trial, part of the trial or a trial site at any time, but agreement on procedures to be followed must be obtained.

If a clinical trial is suspended or prematurely terminated, the investigator must inform the subjects promptly and ensure appropriate therapy and follow-up. As specified by applicable regulatory requirements, the investigator or LEO must promptly inform IRB/IECs and provide a detailed written explanation. Relevant competent authorities must be informed.

The trial must be terminated if the perception of the benefit/risk ratio (judged from clinical signs and symptoms, (S)AEs, and/or remarkable safety laboratory changes) becomes unfavourable for the continuation of the trial.

Reasons for the early closure of a trial site by LEO or investigator may include but are not limited to:

- Failure of the investigator to comply with the protocol, the requirements of the IRB/IEC or local health authorities, LEO's procedures, or GCP guidelines.
 - Inadequate recruitment of subjects by the investigator.

Completion of trial

Investigators will be informed when subject recruitment is to cease. Screening activities will be stopped at a trial site when the total requested number of subjects for the clinical trial has been obtained, irrespective of the specific site's planned inclusion number.

Trial sites will be closed upon trial completion. LEO will undertake arrangements for the collection and disposal of any unused trial material that the investigator is not required to keep in his/her files. A trial site is considered closed when all required documents and trial supplies have been collected and a trial site closure visit has been performed.

When the randomisation code has been broken, the investigators will receive information about the treatment allocation for the subjects randomised at their respective sites and will be asked to record this in the subject's medical record.

Appendix 3I: Responsibilities

The signatory investigator is responsible for the approval of the clinical trial protocol and the CTR on behalf of all clinical trial investigators and as agreed to in a Signatory Investigator Agreement.

The national coordinating investigators are responsible for national issues relating to the clinical trial as agreed to in a National Coordinating Investigator Agreement.

Each participating investigator is responsible for all aspects of the clinical trial conduct at his/her trial site as agreed to in a Clinical Trial Agreement.

Appendix 4: Hanifin and Rajka (1980) diagnostic criteria for AD

Source: Hanifin and Rajka, 1980 (21)

Major Features: must have 3 or more of the following:

- Pruritus
- Typical morphology and distribution:
 - Flexural lichenification or linearity in adults
 - Facial and extensor involvement in infants and children
- Chronic or chronically-relapsing dermatitis
- Personal or family history of atopy (asthma, allergic rhinitis, atopic dermatitis)

Minor Features: should have 3 or more of the following:

- Xerosis
- Ichthyosis, palmar hyperlinearity, or keratosis pilaris
- Immediate (type 1) skin-test reactivity
- Raised serum IgE
- Early age of onset
- Tendency toward cutaneous infections (especially *S. aureus* and herpes simplex) or impaired cell-mediated immunity
- Tendency toward non-specific hand or foot dermatitis
- Nipple eczema
- Cheilitis
- Recurrent conjunctivitis
- Dennie-Morgan infraorbital fold
- Keratoconus
- Anterior subcapsular cataracts
- Orbital darkening
- Facial pallor or facial erythema
- Pityriasis alba
- Anterior neck folds
- Itch when sweating
- Intolerance to wool and lipid solvents
- Perifollicular accentuation
- Food intolerance
- Course influenced by environmental or emotional factors
- White dermographism or delayed blanch

Appendix 5: Guidance for anaphylaxis diagnosis

Source: Sampson et al., 2006 (41)

The National Institute of Allergy and Infectious Diseases (NIAID) and Food Allergy and Anaphylaxis Network (FAAN) Guidance for Anaphylaxis Diagnosis define anaphylaxis as a serious allergic reaction that is rapid in onset and may cause death. They recognise 3 categories of anaphylaxis, with criteria designated to capture from 80% of cases (category 1) to >95% of all cases of anaphylaxis (for all 3 categories).

Clinical criteria for diagnosing anaphylaxis

Anaphylaxis is highly likely when any one of the following 3 criteria are fulfilled:

- 1) Acute onset of an illness (minutes to several hours) with involvement of the skin, mucosal tissue, or both (e.g., generalised hives, pruritus or flushing, swollen lips-tongue-uvula)

AND AT LEAST ONE OF THE FOLLOWING:

- Respiratory compromise (e.g., dyspnoea, wheeze-bronchospasm, stridor, reduced peak expiratory flow [PEF], hypoxemia)
 - Reduced blood pressure (BP) or associated symptoms of end-organ dysfunction (e.g., hypotonia [collapse], syncope, incontinence)
- 2) Two or more of the following that occur rapidly after exposure to a likely allergen for that patient (minutes to several hours):
 - Involvement of the skin-mucosal tissue (e.g., generalised hives, itch-flush, swollen lips-tongue-uvula)
 - Respiratory compromise (e.g., dyspnoea, wheeze-bronchospasm, stridor, reduced PEF, hypoxemia)
 - Reduced BP or associated symptoms (e.g., hypotonia [collapse], syncope, incontinence)
 - Persistent gastrointestinal symptoms (e.g., crampy abdominal pain, vomiting)
 - 3) Reduced BP after exposure to known allergen for that patient (minutes to several hours):
 - Infants and children: low systolic BP (age specific) or greater than 30% decrease in systolic BP

Adults: systolic BP of less than 90 mm Hg or greater than 30% decrease from that person's baseline.

Appendix 6: Eligibility criteria

A short form (maximum 200 characters) version of each of the eligibility criteria for the trial is provided below, to be used when data are submitted to the FDA.

No.	Inclusion criteria
1	Signed and dated informed consent has been obtained prior to any protocol-related procedures
2	Age 18 years and above
3	Diagnosis of AD as defined by Hanifin and Rajka 1980 criteria for AD
4	History of AD for 1 year or more
5	Subjects with a history within 1 year prior to screening of inadequate response to treatment with topical medications or subjects for whom topical treatments are otherwise medically inadvisable
6	AD involvement of 10% (or more) body surface area at screening and baseline (visit 3) according to component A of SCORAD
7	EASI score of 20 (or more) at screening and baseline
8	An IGA score of 3 or more at screening and at baseline
9	A Worst Daily Pruritus numeric rating scale average score of 4 or more during the week prior to baseline
10	Subjects must have applied a stable dose of emollient twice daily (or more, as needed) for at least 14 days before randomisation
11	Women of child-bearing potential must use a highly effective form of birth control, confirmed by the investigator, throughout the trial and at least for 16 weeks after last administration of IMP
12	Documented history of either no previous CSA exposure and not currently a candidate for CSA treatment OR previous exposure to CSA in which case CSA treatment should not be continued or restarted

No.	Exclusion criteria
1	Subjects for whom TCSs are medically inadvisable in the opinion of the investigator
2	Concurrent enrolment in another interventional clinical trial
3	Previous randomisation in a tralokinumab trial
4	Active dermatologic conditions that may confound the diagnosis of AD or would interfere with assessment of treatment, such as scabies, cutaneous lymphoma, or psoriasis
5	Known active allergic or irritant contact dermatitis that is likely to interfere with the assessment of severity of AD
6	Use of tanning beds or phototherapy (NBUVB, UVB, UVA1, PUVA), within 6 weeks prior to randomisation

7	Treatment with immunomodulatory medications or bleach baths within 4 weeks prior to randomisation
8	Treatment with PDE-4 inhibitor within 2 weeks prior to randomisation
9	Receipt of live attenuated vaccines within 30 days prior to the date of randomisation and during the trial including the safety follow-up period
10	Receipt of any marketed or investigational biologic agent (e.g. cell-depleting agents or dupilumab) within 6 months prior to randomisation or until cell counts return to normal, whichever is longer
11	Receipt of any investigational non-biologic agent within 5 half-lives prior to randomisation
12	Receipt of blood products within 4 weeks prior to screening
13	Major surgery within 8 weeks prior to screening, or planned in-patient surgery or hospitalisation during the trial period
14	Known or suspected hypersensitivity to any component of the IMP or AxMP formulation
15	History of any active skin infection within 1 week prior to randomisation
16	History of a clinically significant infection (systemic infection or serious skin infection requiring parenteral treatment) within 4 weeks prior to randomisation
17	A helminth parasitic infection within 6 months prior to the date informed consent is obtained that has not been treated with, or has failed to respond to, standard of care therapy
18	History of anaphylaxis following any biological therapy
19	History of immune complex disease
20	History of cancer
21	Tuberculosis requiring treatment within the 12 months prior to screening. Evaluation will be according to local guidelines as per local standard of care
22	History of any known primary immunodeficiency disorder including a positive HIV test at screening, or the subject taking antiretroviral medications
23	History of chronic alcohol or drug abuse within 12 months prior to screening, or any condition associated with poor compliance as judged by the investigator
24	History of attempted suicide or at significant risk of suicide (either in the opinion of the investigator or on the C-SSRS)
25	Any disorder which is not stable and in the investigator's opinion could affect the safety of the subject, influence the findings of the trial, or impede the subject's ability to complete the trial
26	Any abnormal finding which in the investigator's opinion may put the subject at risk, influence the results of the trial, or influence the subject's ability to complete the trial
27	Alanine aminotransferase (ALT) or aspartate aminotransferase (AST) level 2.0 times the ULN (upper limit of normal) or more at screening

28	Positive HBsAg, HBsAb, HBcAb, or anti-HCV serology at screening. Subjects with positive HBsAb may be randomised provided they are hepatitis B vaccinated and have negative HBsAg and HBcAb
29	Subjects who are not willing to abstain from donating blood and/or plasma from the time of informed consent and for 16 weeks (5 half-lives) after last dose of IMP
30	Subjects who are legally institutionalised
31	Pregnant, breastfeeding, or lactating women
32	Employees of the trial site or any other individuals directly involved with the planning or conduct of the trial, or immediate family members of such individuals

Appendix 8: Clinical Trial Protocol Addendum COVID-19

1 Rationale for clinical trial protocol addendum

The current COVID-19 pandemic warrants many subjects in the ECZTRA 7 trial to stay at home to comply with authority issued preventive measures. This make visits to the sites challenging, and in some cases impossible. To follow authorities restrictions and to safeguard the subjects in ECZTRA 7 as well as providing continued therapy to secure the scientific integrity, this clinical trial protocol addendum is installed to provide an opportunity for subjects to continue treatment with tralokinumab via home-use (self-injection).

No safety issues have been observed in subjects who applied home-use of IMP after training by site staff in previous or ongoing clinical trials with tralokinumab. Therefore, no safety issues are expected regarding home-use of IMP in ECZTRA 7.

2 GCP statement

Normal GCP procedures are followed for this protocol addendum. Subjects will be verbally informed and verbally consent to providing contact details (name, address, and telephone number) for shipping purposes.

3 eCRF recording

It must be recorded in the eCRF if the visit was conducted as a home-visit.

If the subject is reached by telephone/video contact and collection of AEs, concomitant medication and pregnancy test result (if applicable) are assessed, "Visit date" must be documented in the eCRF. All other assessments should be marked "Not done". The log line "If not done, specify reason" must be answered with "COVID-19". In addition, in the "Comments log", one log line per visit should be entered with "COVID-19" – as reason for only partly performed assessments at the visit.

If no contact can be established between site and subject at a given visit, this must be recorded as a missed visit in the eCRF ("Not done"). The log line "If not done, specify reason" must be answered with "COVID-19".

4 Description of visit scenarios

Without compromising the safety of subjects and site personnel, it is expected that efforts are made to secure attendance at sites for the Week 16 and Week 26 visits, securing important efficacy and safety assessments for the trial. Dependant on national guidelines regarding

COVID-19 and subject preferences, the remaining visits can follow three different scenarios as described below:

- 1) The subject is not restricted from attending visits at the clinic and continue to follow all procedures specified in the protocol.
- 2) The subject is still able to come to the clinic, but may foresee difficulties attending visits to the clinic going forward. In this case the following procedures must take place and be document in source documentation:
 - a. Subject is verbally informed using the Participant Information Sheet and agrees to home-use of IMP.
 - b. Site staff allocates IMP and TCS for subject using the EDC system (RAVE®) for the current visit + 2 additional visits.
 - c. Subject is trained by site staff in home-use of IMP (see Section 5.1) by the unblinded HCP. The subject then self-injects IMP under supervision of the unblinded HCP. The remaining part of the visit takes place as per protocol.
 - d. Site staff provide the following items to the subject:
 - i. Participant Information Sheet for home use.
 - ii. Instructions for Use.
 - iii. Log of Drug Administration.
 - iv. The proper amount of IMP (see bullet c) in a cooling bag.
 - v. The proper amount of TCS (see bullet c).
 - vi. One sharp-bin container.
 - vii. Sanitisers: alcohol wipes, cotton balls or gauze.
 - viii. For female subjects of child-bearing potential: one urine pregnancy test kit and Urine Pregnancy Test Instruction.
 - e. The following visits must be conducted via phone with collection of AEs, assessment of concomitant medication, and urine pregnancy test results (if applicable) before IMP is self-injected. The subject is reminded to complete the eDiary and to start using the TCS tubes allocated for the next period.

- 3) Subject is not able to attend visits at the clinic:
- a. Site staff informs subject about the possibility of home-use as described in the Participant Information Sheet for home-use.
 - b. Subject is verbally informed about home-use of IMP and verbally consents to providing contact details (name, address, and telephone number) to the courier for shipping purposes.
 - c. Site staff allocates IMP and TCS for subject using the EDC system (RAVE®) for the 3 visits. In case needed, IMP and TCS can be dispensed for one additional visit.
 - d. Site staff sends the following items by a LEO-approved courier company:
 - i. Participant Information Sheet for home use.
 - ii. Instructions for Use.
 - iii. Log of Drug Administration.
 - iv. The proper amount of IMP (see bullet c) in a cooling bag.
 - v. The proper amount of TCS (see bullet c).
 - vi. One sharp-bin container.
 - vii. Sanitisers: alcohol wipes, cotton balls or gauze.
 - viii. For female subjects of child-bearing potential: one urine pregnancy test kit and Urine Pregnancy Test Instruction.
 - e. Site staff contacts the subject (by video-call) and ensures the following:
 - i. Confirms that the Participant Information Sheet has been read, understood, and agreed to.
 - ii. Subject is asked about pregnancy test outcome, concomitant medication use, and adverse events.
 - iii. Subject is being instructed in home-use of IMP.
 - iv. The subject self-injects IMP under supervision of the site staff.

- v. The subject is reminded to complete the eDiary and to start using the TCS tubes allocated for the next period.
- f. Site staff documents all of the above in the medical record at the clinic.
- g. Site staff enters all available information into the EDC system (RAVE[®]), see Section 3.

5 Home-use of IMP

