9.2 Administration of trial products

9.2.1 Administration of IMP

The IRT will assign the required kit numbers for each subject at each dispensing visit.

Dosing visits are shown in the schedule of trial procedures (Section 4). The last administration of IMP will occur at Week 24. To ensure blinding, both treatment groups will receive the same number of injections at each visit.

The first day of dosing is considered Day 0 (visit 3, baseline). Each subject will receive 4 SC injections (each of 1 mL) to receive a loading dose of tralokinumab or placebo. At subsequent visits in the treatment period, each subject will receive 2 SC injections (each of 1 mL).

Hence, subjects in the treatment period will receive either:

- Tralokinumab 300 mg Q2W: tralokinumab 600 mg (4 mL) at baseline, then tralokinumab 300 mg (2 mL) Q2W.
- Placebo Q2W: placebo (4 mL) at baseline, then placebo (2 mL) Q2W.

IMP will be administered by a qualified, unblinded health care professional (HCP; see Section 9.3.1 for blinding details). A minimum interval of 7 days is required between 2 dosing visits. No specific treatment for an overdose is recommended. The investigator will use clinical judgement to treat any overdose if necessary. See Section 13.6.2 for further details regarding overdose.

The injections will be administered into the SC tissue of the upper arm, anterior thigh, or abdomen, separated by at least 3 cm. The injection site must be recorded in the source documents at each treatment visit and recorded in the eCRF.

Further details on IMP administration are provided in the trial product handling manual. IMP administration must be carried out according to these instructions.

After IMP administration

For the first 3 IMP dosing visits in the treatment period (i.e., Weeks 0, 2, and 4), subjects will be monitored after IMP administration for immediate drug reactions for a minimum of 30 minutes with vital signs taken at 30 minutes or until stable, whichever is later. Vital signs will be documented in the eCRF.

As with any antibody, allergic reactions to dose administration are possible. The World Allergy Organization has categorised anaphylaxis into 2 subgroups: allergic anaphylaxis

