(mediated by an immunologic mechanism) and nonallergic anaphylaxis (which has a nonimmunologic cause) (23). The clinical criteria for defining anaphylaxis for this trial are listed in [Appendix 5](#). Appropriate drugs, such as epinephrine, antihistamines, corticosteroids, etc., and medical equipment to treat acute anaphylactic reactions must be immediately available at the trial sites, and trial personnel should be trained to recognise and respond to anaphylaxis according to local guidelines.

If an anaphylactic reaction occurs, a blood sample will be drawn from the subject as soon as possible after the event, at 60 minutes \pm 30 minutes after the event, and at discharge, for analysis of serum tryptase at the central laboratory.

Conditions requiring rescheduling of IMP administration

If any of the following should occur, the investigator should reschedule the visit and IMP should not be administered until the rescheduled visit:

- The subject has an intercurrent illness that, in the opinion of the investigator, may compromise the safety of the subject in the trial (e.g., viral illnesses).
- The subject is febrile (defined as $\geq 38^{\circ}\text{C}$) within 72 hours prior to IMP administration.

If the trial visit cannot be rescheduled to maintain minimum of 7 days to subsequent dose, the sponsor's medical expert should be contacted.

LEO does not recommend specific treatment for an overdose. The investigator will use clinical judgement to treat any overdose if necessary.

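### Appendix 8 sets no earliest home-use visit, which conflicts with the unwaived 30-minute post-dose monitoring rule for the Week 2 and Week 4 doses

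*Protocol*

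**What the plan says.** **The monitoring rule.** Section 9.2.1 states: "For the first 3 IMP dosing visits in the treatment period (i.e., Weeks 0, 2, and 4), subjects will be monitored after IMP administration". The minimum is 30 minutes, with vital signs. Section 11.4.1 and Panel 2 footnote 5 repeat the rule, and Section 5.6 counts it among the measures that protect subjects, specifically against hypersensitivity. Section 9.2.1 also requires that "medical equipment to treat acute anaphylactic reactions must be immediately available at the trial sites". SAP Section 6.7.2 (21-Oct-2020), which is later than Amendment 3 (15-Jun-2020), still describes the post-dose vital signs and plans to list them.

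**The home-use addendum.** Appendix 8 Section 4 asks sites to try to secure attendance at Weeks 16 and 26. For everything else, "the remaining visits can follow three different scenarios as described below".
- Scenario 2 (the subject can attend now but expects difficulty later): IMP is allocated "for the current visit + 2 additional visits". After that, "The following visits must be conducted via phone with collection of AEs, assessment of concomitant medication", together with any pregnancy test result, all before the self-injection.
- Scenario 3 (the subject cannot attend): IMP is allocated "for the 3 visits. In case needed, IMP and TCS can be dispensed for one additional visit". On a video call, "The subject self-injects IMP under supervision of the site staff". No duration is given.

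Appendix 8 Section 3 covers recording. At a telephone or video visit, AEs, concomitant medication and any pregnancy test are collected. "All other assessments should be marked" as not done, with COVID-19 as the reason.

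**The concern.** Weeks 2 and 4 are among the visits that Appendix 8 opens to home use, and they are also two of the three doses that must be followed by monitored observation. Nothing in Appendix 8 separates the two. It states that TCS use, emollient use and the pregnancy-test schedule are unchanged, but it has no matching statement about early-dose monitoring.

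At stake is a named safety precaution at the second and third doses. A site that uses scenario 2 or 3 at those visits has no means of taking vital signs, no stated observation period, and none of the emergency drugs and equipment that Section 9.2.1 requires at sites. In scenario 2, no staff contact after the injection is specified. In scenario 3, the injection itself is watched, so what is missing is the observation time and the vital signs, not all observation.

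**Working it through.** The plan gives no figure to reproduce. The check sets the monitored doses against the doses that each scenario can place at home.

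**Inputs.** Monitored doses: Weeks 0, 2 and 4 (Section 9.2.1). Dosing is every 2 weeks, with the last dose at Week 24 (Section 7.1). Scenario 2 covers the current on-site visit plus 2 home visits. Scenario 3 covers 3 home visits, with an optional fourth (Appendix 8 Section 4). Assumption: the Week 0 dose is always given on site, because randomisation takes place there.

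| Entry | Home doses | Monitored doses at home |
|---|---|---|
| Scenario 2, entered at Week 0 | Weeks 2, 4 | 2 of 3 |
| Scenario 2, entered at Week 2 | Weeks 4, 6 | 1 of 3 |
| Scenario 2, entered at Week 4 | Weeks 6, 8 | 0 of 3 |
| Scenario 3, from Week 2 | Weeks 2, 4, 6 | 2 of 3 |
| Scenario 3, from Week 4 | Weeks 4, 6, 8 | 1 of 3 |
| Scenario 3, from Week 6 | Weeks 6, 8, 10 | 0 of 3 |

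The optional fourth visit in scenario 3 falls at Week 8 or later, so it changes no row.

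**Can both rules be met at a home dose?**
1. *Observation time.* In scenario 2 the phone checks come before the injection, and the addendum's section on injections repeats that AE assessment comes first. Scenario 3 supervises the injection but does not say for how long.
2. *Vital signs.* Neither scenario has a step for taking them, and the recording rule classes them as not done.
3. *Earliest visit.* None is stated anywhere in Appendix 8. Its training section asks for a supervised injection on one or more occasions, which does not amount to three on-site doses.

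The rule in Section 9.2.1 therefore cannot be met at a Week 2 or Week 4 dose given under Appendix 8 as written.

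**Reach of a Week 6 limit.** Doses from Week 2 to Week 24 every 2 weeks: 12. Less Week 16, which sites are asked to keep: 12 − 1 = 11 home-eligible dosing visits. Weeks 2 and 4 return to the site: 2/11 = 18%. Unchanged: 11 − 2 = 9.

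**The case against.** The strongest reply is that the monitoring rule was never waived. It stands without conditions in the same amended protocol, and the later SAP still plans for its data. A specific rule for three named doses can be read as governing a general phrase about remaining visits, and a site that skipped the monitoring would then breach Section 9.2.1. This stands. A reader might infer that Appendix 8 permits sites to drop the monitoring; the documents do not say so. The not-done instruction is an eCRF recording rule and authorises nothing. What remains is a conflict: the rule binds, but the home procedure offers no way to comply.

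A second reply is that exposure is speculative. Appendix 8 is for subjects who continue treatment. The 2-of-3 case under scenario 2 needs someone trained to self-inject at the loading-dose visit. Amendment 3's summary of changes also mentions many subjects moving on to the extension trial, so recruitment may have been well advanced. This also stands, with limits. A Week 2 dose is continued treatment too, and the date on which the addendum took effect is not given.

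Third, Appendix 8 reports no safety issues with trained home use in other tralokinumab trials, and training covers emergencies. That is reassuring, but the text does not say whether that experience included second or third doses, and training does not supply observation or vital signs.

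Finally, the Trial Product Handling Manual and the home-use instructions were not available to us and may hold a limit. Appendix 8 neither states one nor says that they do.

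**Conclusion.** The conflict is real and small. Appendix 8 allows up to 2 of the 3 monitored doses to move home, under a procedure that cannot deliver the monitoring that Sections 9.2.1 and 11.4.1 and Panel 2 footnote 5 still require. The counts describe possible entry points. A reader might take them as a measure of risk, or as evidence that subjects were dosed without monitoring. The documents support neither: they give no number of subjects who had yet to receive the Week 4 dose when the addendum took effect, and that number may be zero. No endpoint, estimand or test is affected. The conclusion assumes that the unseen site documents do not already set an earliest home-use visit. If they do, only the cross-reference is missing. The repair is worth making because it removes a contradiction over a safety precaution at little cost.

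**What to change.** Add to Appendix 8 Section 4:

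> Home-use may start only after the third on-site dose (from Week 6). The Week 2 and Week 4 doses are given at the site with the monitoring in Section 9.2.1, which is unchanged.

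Cross-reference this in Sections 9.2.1 and 11.4.1 and in Panel 2 footnote 5.

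**Cost.** Two short sentences, three cross-references, and 2 of 11 home-eligible dosing visits back on site. The downside is that a subject who cannot attend at Week 2 or Week 4 misses or delays that dose, and starts home use later as a result. Under Section 14.3.1, missing those two doses because of the pandemic is not by itself a prolonged interruption. It becomes one if the next dose is also missed or is more than 7 days late.

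**Optional fallback.** If the sponsor wants a route for subjects who cannot attend, the roles need to be split. Section 9.3.1 confines the unblinded HCP to handling and giving the IMP and keeps that person out of subject management and assessments. Blinded staff, in turn, should not see the visually distinct syringes. The unblinded HCP should therefore supervise only the injection by video. Once the syringes are out of view, blinded site staff take over the call, observe for at least 30 minutes and document it. For these two doses this would replace the phone contact in scenario 2 and the unspecified site staff in scenario 3. It costs about 30 minutes of observation per dose, so at most 2 × 30 = 60 minutes per subject. It still gives no vital signs and no emergency drugs at hand, and it relaxes a rule that is unconditional today, so it should be the exception.
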